2.2 Protocol Deviations

The general categories listed in [Appendix 9.1](#) will be considered important protocol deviations (IPDs) and will be either observable and provided by AstraZeneca or programmatically derived from the electronic case report form (eCRF) data.

Patients who receive the wrong treatment at any time will be included in the safety analysis set as described in Section 2.1. During the study, decisions on how to handle errors in treatment dispensing (with regard to continuation/discontinuation of study treatment or, if applicable, analytically) will be made on an individual basis with written instruction from the study team leader and/or statistician.

The important protocol deviations will be listed and summarised by randomised treatment group and discussed in the clinical study report (CSR) as appropriate. None of the deviations will lead to patients being excluded from the analysis sets described in Section 2.1 (with the exception of the PK analysis set, if the deviation is considered to impact upon PK).

In addition to the IPDs, other study deviations captured from the case report form (CRF) module for inclusion/exclusion criteria will be tabulated and listed. Any other deviations from monitoring notes or reports will be reported in an appendix to the CSR.

Depending on the extent of any impact, summaries of data relating to patients diagnosed with COVID-19, and impact of COVID-19 on study conduct may be generated including:

- Disposition (discontinued IP due to COVID-19 and withdrew study due to COVID-19)
- Deviations (overall deviations plus if due to COVID-19 and not due to COVID-19)
- Summary of COVID-19 disruption (visit impact, drug impacted)
- Listing for patients affected by the COVID-19 pandemic.

3 PRIMARY AND SECONDARY VARIABLES

3.1 Derivation of RECIST Visit Responses

For all patients, the RECIST tumour response data will be used to determine each patient's visit response according to RECIST version 1.1. It will also be used to determine if and when a patient has progressed in accordance with RECIST and their best objective response to study treatment.

Baseline radiological tumour assessments are to be performed no more than 28 days before the start of randomised treatment and ideally as close as possible to the start of study treatment.

For patients who cross-over to savolitinib plus osimertinib based on confirmed objective disease progression during the initial randomised treatment period (including patients who have already crossed over based on confirmed PD prior to CSP V3.0) the baseline scan for response endpoints during the cross-over period will be the progression scan on savolitinib plus placebo, which should be acquired within 28 days of the start of treatment in the cross-over period. Scheduled RECIST 1.1 tumour assessments are not required for these patients, and the subsequent assessment of disease progression will be based on standard-of-care scan or investigator determined clinical progression.

For patients who cross-over after study unblinding and who have not objectively progressed during the initial randomised treatment period, scheduled RECIST 1.1 tumour assessments are

required using initial randomisation as baseline. Patients who then discontinue study intervention after cross-over for reasons other than investigator-confirmed disease progression will continue scheduled RECIST 1.1 tumour assessments until objective disease progression per RECIST 1.1 as assessed by investigator, unless they withdraw consent to the entire study. These tumour assessments are then performed every 6 weeks following the start of study treatment up to 24 weeks relative to initial randomisation, then every 8 weeks until objective disease progression.

If an unscheduled assessment is performed, and the patient has not progressed, every attempt should be made to perform the subsequent assessments at their scheduled visits. This schedule is to be followed in order to minimise any unintentional bias caused by some patients being assessed at a different frequency than other patients.

From the investigator's review of the imaging scans, the RECIST tumour response data will be used to determine each patient's visit response according to RECIST version 1.1. At each visit, patients will be programmatically assigned a RECIST 1.1 visit response of complete response (CR), partial response (PR), stable disease (SD) or progressive disease (PD), using the information from target lesions (TLs), non-target lesions (NTLs) and new lesions and depending on the status of their disease compared with baseline and previous assessments. If a patient has had a tumour assessment that cannot be evaluated, then the patient will be assigned a visit response of not evaluable (NE) (unless there is evidence of progression in which case the response will be assigned as PD).

Please refer to [Section 3.1.1](#) for the definitions of CR, PR, SD and PD.

RECIST outcomes (i.e. progression free survival [PFS], objective response rate [ORR] etc.) will be calculated programmatically for the site investigator data (see [Section 3.2](#)) from the overall visit responses.

Patients with measurable or non-measurable disease assessed at baseline by computed tomography (CT) / magnetic resonance imaging (MRI) will be entered in this study.

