
To evaluate the efficacy of savolitinib plus osimertinib in patients who cross-over after progression on savolitinib plus placebo. ^a
	
 • Objective response rate is defined as the proportion of patients with measurable disease who have a CR or PR as determined by the investigator at the local site per RECIST 1.1. • Progression-free survival is defined as time from the first dose in the cross-over period until progression per RECIST 1.1 as assessed by the investigator or death due to any cause. • Duration of response is defined as the time from the date of first documented response during the cross-over period until date of documented progression per RECIST 1.1 as assessed by the investigator or death in the absence of disease progression. • Tumour size assessment is defined as the percentage change from baseline in TLs at 12 weeks per RECIST 1.1 as assessed by the investigator.

To evaluate the PK of savolitinib and osimertinib.
	
Plasma concentrations of savolitinib, osimertinib, and their metabolites.

To determine the prevalence of ctDNA clearance after savolitinib plus osimertinib or savolitinib plus placebo treatment in this patient population.
	
Total clearance in EGFR mutations at 6-weeks after therapy initiation (percentage and absolute change from baseline in EGFR mutation allele frequencies).

Safety objective:
	
Safety endpoints/variables:

To evaluate the safety and tolerability of savolitinib plus osimertinib or savolitinib plus placebo.
	
Safety and tolerability will be evaluated in terms of AEs, SAEs and discontinuation rate due to AEs. Clinical chemistry/haematology including LFTs, ECHOs, ECGs and vital signs including blood pressure and heart rate.

Tertiary/exploratory objectives:
	
Tertiary/exploratory endpoints/variables:

^a Baseline for ORR, PFS, DoR and tumour size assessments of patients who cross-over to savolitinib plus osimertinib from savolitinib plus placebo will be the progression scan on savolitinib plus placebo acquired within 28 days of the start of treatment in the cross-over period.

CCI

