2 ANALYSIS SETS

2.1 Definition of Analysis Sets

Patients will be assigned to the following analysis sets prior to any analyses being performed.

Full Analysis Set (FAS)

The FAS will include all randomised patients with treatment groups assigned in accordance with the randomisation, regardless of the treatment actually received. Patients who were randomised but did not subsequently receive treatment are included in the FAS. The analysis of data using the FAS therefore follows the principles of intention to treat.

The FAS will be the primary population for reporting efficacy data and to summarise baseline characteristics.

Safety analysis set (SAF)

The Safety analysis set will consist of all randomised patients who received any amount of study treatment. Safety data will not be formally analysed but summarised using the safety analysis set according to the treatment received. If a patient receives any amount of an experimental therapy, they will be summarised in the treatment group corresponding to the first experimental treatment they received.

Cross-over analysis set

The Cross-over analysis set will consist of all patients who were randomised to savolitinib in combination with placebo and received at least one dose of savolitinib plus osimertinib in the cross-over period of the study.

It will be used as the population for reporting the efficacy and safety data for patients who crossed over to treatment with savolitinib plus osimertinib following objective progression on savolitinib plus placebo.

PK analysis set

All patients who receive at least one dose of savolitinib or osimertinib as per the protocol, for whom there are at least one reportable PK concentration without any protocol deviation impacting PK, will be included in the PK analysis set. If a patient receives any amount of an experimental therapy, they will be summarised in the treatment group corresponding to the first experimental treatment they received.

Monotherapy analysis set

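### The SAP contradicts itself on who is in the cross-over efficacy analysis, from which baseline and with which progression event, so a response reached on monotherapy can count as a cross-over response

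*SAP*

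**What the plan says.** **Objective and endpoints (Section 1.1, Table 1).** The secondary objective reads "To evaluate the efficacy of savolitinib plus osimertinib in patients who cross-over after progression on savolitinib plus placebo". Its endpoints are ORR, PFS, DoR and target-lesion change at 12 weeks, all per RECIST 1.1:

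- ORR: "Objective response rate is defined as the proportion of patients with measurable disease who have a CR or PR as determined by the investigator". This wording does not limit the response to scans taken after cross-over.
- PFS: "Progression-free survival is defined as time from the first dose in the cross-over period until progression per RECIST 1.1 as assessed by the investigator". Deaths also count as events.
- DoR: "Duration of response is defined as the time from the date of first documented response during the cross-over period until date of documented progression". Deaths also end a response.
- Footnote a gives one baseline for ORR, PFS, DoR and week 12 tumour size alike: "tumour size assessments of patients who cross-over to savolitinib plus osimertinib from savolitinib plus placebo will be the progression scan". No exception is made for a patient without one.

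**Analysis set (Section 2.1).** The cross-over analysis set takes every patient randomised to savolitinib plus placebo who "received at least one dose of savolitinib plus osimertinib in the cross-over period of the study". The next sentence describes its use as reporting patients who crossed over following objective progression. Table 2 assigns the cross-over efficacy endpoints to this set.

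**Two routes (Sections 1.2, 3.1 and 5).** Patients may cross over after progression or, once the study is unblinded, without it. For the progressed route Section 3.1 says: "Scheduled RECIST 1.1 tumour assessments are not required for these patients, and the subsequent assessment of disease progression will be based on standard-of-care scan". The alternative it allows is clinical progression determined by the investigator. For the non-progressed route, scheduled RECIST assessments are "required using initial randomisation as baseline".

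**Analysis (Section 4.2.10).** Selected analyses, including efficacy, are repeated on the cross-over set where the data suffice. There is no split by route.

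**The concern.** The objective asks whether adding osimertinib produces responses in patients whose disease has progressed on savolitinib plus placebo. Two features of the text work against that.

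First, the set can contain patients who had not progressed and who carry the randomisation baseline. If such a patient was already in partial response on monotherapy, the first scan after the switch is still a partial response against that baseline, even if nothing changed after osimertinib was added. Counting it credits the combination with a monotherapy response.

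Second, the patients the objective is about have no scheduled RECIST scans, and their progression may be a clinical judgement. Table 1 nevertheless defines PFS and DoR by RECIST 1.1 progression. The SAP does not say whether clinical progression is an event, a censoring or neither.

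Two programmers could produce different cross-over tables from this text, each with a defensible reading.

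**Working it through.** The SAP states no figure on this point, so there is nothing to reproduce. The check has three parts.

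**1. The passages side by side**

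| Item | Progressed before cross-over | Not progressed before cross-over |
|---|---|---|
| Covered by the Table 1 objective | Yes | No |
| Admitted by the Section 2.1 membership rule | Yes | Yes |
| Covered by the Section 2.1 purpose sentence | Yes | No |
| Baseline, Table 1 footnote a | Progression scan | None exists |
| Baseline, Section 3.1 | Progression scan | Initial randomisation |
| Scheduled RECIST scans, Section 3.1 | Not required | Required |
| Later progression, Section 3.1 | Standard-of-care scan or clinical | Objective, RECIST 1.1 |

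The two problems fall on different groups: missing scheduled scans on the progressed group, carry-over of response on the non-progressed group.

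**2. Carry-over under the SAP's own response rules**

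Inputs from Section 3.1.1: PR is a decrease of at least 30% from baseline, provided PD is not met; PD is an increase of at least 20% and at least 5 mm from the nadir; percentages are rounded to one decimal place. Assumed patient: target-lesion sum 100 mm at randomisation, 60 mm at nadir and at the switch, no new lesions and no non-target progression.

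Change from randomisation = (x − 100)/100. Change from switch = (x − 60)/60.

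| Scan x (mm) | From randomisation | Response | From switch | Response |
|---|---|---|---|---|
| 60 | −40.0% | PR | 0.0% | SD |
| 65 | −35.0% | PR | +8.3% | SD |
| 68 | −32.0% | PR | +13.3% | SD |
| 70 | −30.0% | PR | +16.7% | SD |
| 72 | −28.0% | PD (+20.0%, 12 mm from nadir) | +20.0% | PD |

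Across 60 to 70 mm the patient is a responder on one baseline and stable on the other, including when the tumour has grown by 16.7% since the switch. Cross-over DoR would start at the first such scan.

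If k of n patients carry over a PR and nobody newly responds, the reported ORR is k/n where the number of new responses is 0. The SAP gives neither n nor k. Over assumed values, k = 1 to 3 gives 1/6 to 3/6 = 17% to 50% for n = 6, 10% to 30% for n = 10, and 1/14 to 3/14 = 7% to 21% for n = 14. The Clopper-Pearson 95% interval for 3/10 is 6.7% to 65.2%. These figures show what is possible, not what is expected.

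**3. Progression event in the progressed group**

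Section 3.1 derives RECIST outcomes by program from overall visit responses. Section 3.1.2 says symptomatic progression does not describe non-target progression. Two further rules presume a schedule: the two-missed-visits censoring in Section 3.2.2, and the window of one week either side of the scheduled visit for week 12 in Section 3.2.6. No version of any of these is given for patients followed by standard-of-care scans, and no rule turns clinical progression into a PFS event or excludes it.

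**The case against.** The strongest reply is that three places (the objective, footnote a and the purpose sentence in Section 2.1) confine cross-over efficacy to post-progression patients. On that reading no carry-over arises, because a non-progressed patient has no progression scan. The randomisation baseline in Section 3.1 could simply mean that the main RECIST follow-up continues. This fits the main PFS definition in Section 3.2.2, which runs from randomisation whatever therapy follows. Section 3.1 never says that this baseline feeds cross-over ORR.

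This reading is plausible, and the text does not show that pooling was intended. It does not settle the matter. The membership rule is what a programmer implements, Table 2 attaches the efficacy endpoints to that set, and Section 4.2.10 adds no restriction. If the randomisation baseline is not meant for the cross-over endpoints, patients in the set have no baseline for them at all.

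A reader might infer that the endpoints cannot be derived, or that progressed patients have no RECIST data. The SAP does not support that. Scheduled scans are not required, but standard-of-care scans are foreseen, the ORR and PFS analyses use all scans whether scheduled or not (Sections 4.2.2.1 and 4.2.3.1), and Section 4.2.10 applies only where data suffice. The assessment procedures for patients who switch under CSP V3.0 are also referred to CSP Table 2. That last qualification, however, concerns the amount of data. It does not decide who is analysed, from which baseline, or what counts as progression.

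**Conclusion.** The contradiction is real. As written, the SAP permits a partial response reached on savolitinib plus placebo to count in cross-over ORR and to start cross-over DoR, against its own objective and footnote. Each response carried over this way adds a responder that the added osimertinib did not produce. Separately, cross-over PFS and DoR in progressed patients are poorly determined by the stated rules, because the progression that will be recorded is not the progression in the definition.

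The size is unknown. The worked patient and the values of n and k are assumptions, and k/n further assumes no new response in any patient. It would be wrong to attach a particular inflated response rate to this trial.

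Nor do these passages show that the primary ORR in the full analysis set is affected. Cross-over efficacy is a secondary, descriptive analysis. The point should be fixed before the final analysis, but it does not threaten the main result.

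**What to change.** 1. In Sections 2.1 and 4.2.10, add a flag for route of cross-over. Restrict cross-over ORR, DoR, PFS and week 12 tumour size to patients who crossed over after objective progression, with the progression scan as baseline. Show how many of them have target-lesion measurements after cross-over.
2. Report patients who crossed over without progression separately. State that a response first reached before the first cross-over dose is not a cross-over response.
3. Reconcile Table 1 with Section 3.1 by stating whether investigator-determined clinical progression is a cross-over PFS event, and label the endpoint to match.

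The cost is SAP wording and one derived flag. No new scans and no change to patient management are involved. The drawback is fewer patients in each cross-over table.

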3.1.1 Target lesions (TLs) – site investigator data

Measurable disease is defined as having at least one measurable lesion, not previously irradiated, which is ≥ 10 mm in the longest diameter (LD), (except lymph nodes which must have short axis ≥ 15 mm) with CT or MRI and which is suitable for accurate repeated measurements. A patient can have a maximum of five measurable lesions recorded at baseline with a maximum of two lesions per organ (representative of all lesions involved and suitable for accurate repeated measurement) and these are referred to as TLs. If more than one baseline scan is recorded, then measurements from the one that is closest and prior to randomisation will be used to define the baseline sum of TLs. It may be the case that, on occasion, the largest lesion does not lend itself to reproducible measurement, in which circumstance the next largest lesion, which can be measured reproducibly, should be selected.

All other lesions (or sites of disease) not recorded as TL should be identified as NTLs at baseline. Measurements are not required for these lesions, but their status should be followed at subsequent visits.

Note: For patients who do not have measurable disease at entry (i.e. no TLs) but have non-measurable disease, evaluation of overall visit responses will be based on the overall NTL assessment and the absence/presence of new lesions (see [Section 3.1.3](#) for further details). If a patient does not have measurable disease at baseline, then the TL visit response will be not applicable (NA).

Table 3 TL Visit Responses (RECIST 1.1)

Visit Responses	Description
Complete response (CR)	Disappearance of all TLs. Any pathological lymph nodes selected as TLs must have a reduction in short axis to < 10mm.
Partial response (PR)	At least a 30% decrease in the sum of diameters of TLs, taking as reference the baseline sum of diameters as long as criteria for PD are not met.
Progressive disease (PD)	A $\geq 20\%$ increase in the sum of diameters of TLs and an absolute increase of $\geq 5\text{mm}$, taking as reference the smallest sum of diameters since treatment started including the baseline sum of diameters.
Stable disease (SD)	Neither sufficient shrinkage to qualify for PR nor sufficient increase to qualify for PD.
Not evaluable (NE)	Only relevant in certain situations (i.e. if any of the TLs were not assessed or not evaluable or had a lesion intervention at this visit; and scaling up could not be performed for lesions with interventions). Note: If the sum of diameters meets the progressive disease criteria, progressive disease overrides not evaluable as a TL response.
Not applicable (NA)	No TLs are recorded at baseline.

Rounding of TL data

For calculation of PD and PR for TLs percentage changes from baseline and previous minimum should be rounded to one d.p. before assigning a TL response. For example, 19.95% should be rounded to 20.0% but 19.94% should be rounded to 19.9%.

Missing TL data

For a visit to be evaluable then all TL measurements should be recorded. However, a visit response of PD should still be assigned if any of the following occurred:

- A new lesion is recorded
- An NTL visit response of PD is recorded
- The sum of TLs is sufficiently increased to result in a 20% increase, and an absolute increase of ≥ 5 mm, from nadir even assuming the non-recorded TLs have disappeared.

Note: the nadir can only be taken from assessments where all the TLs had a LD recorded.

If there is at least one TL measurement missing and a visit response of PD cannot be assigned, the visit response is NE.

If all TL measurements are missing then the TL visit response is NE. Overall visit response will also be NE, unless there is a progression of non-TLs or new lesions, in which case the response will be PD.

Lymph nodes

For lymph nodes, if the size reduces to < 10 mm then these are considered non-pathological. However, a size will still be given and this size should still be used to determine the TL visit response as normal. In the special case where all lymph nodes are < 10 mm and all other TLs are 0mm then although the sum may be > 0 mm the calculation of TL response should be overwritten as a CR.

TL visit responses subsequent to CR

Only CR, PD or NE can follow a CR. If a CR has occurred, then the following rules at the subsequent visits must be applied:

- Step 1: If all lesions meet the CR criteria (i.e. 0mm or < 10 mm for lymph nodes) then response will be set to CR irrespective of whether the criteria for PD of TL is also met i.e. if a lymph node LD increases by 20% but remains < 10 mm.
- Step 2: If some lesion measurements are missing but all other lesions meet the CR criteria (i.e. 0mm or < 10 mm for lymph nodes) then response will be set to NE irrespective of whether, when referencing the sum of TL diameters, the criteria for PD are also met.
- Step 3: If not all lesions meet the CR criteria (i.e. a pathological lymph node selected as TL has short axis > 10 mm or the reappearance of previously disappeared lesion) or a new lesion appears, then response will be set to PD
- Step 4: If after steps 1 – 3 a response can still not be determined the response will be set to remain as CR.

TL too big to measure

If a TL becomes too big to measure this should be indicated in the database and a size ('x') above which it cannot be accurately measured should be recorded. If using a value of x in the calculation of TL response would not give an overall visit response of PD, then this will be flagged and reviewed by the study team blinded to treatment assignment. It is expected that a visit response of PD will remain in the vast majority of cases.

TL too small to measure

If a TL becomes too small to measure, then this will be indicated as such on the case report form and a value of 5mm will be entered into the database and used in TL calculations. However, a smaller value may be used if the radiologist has not indicated 'too small to measure' on the case report form and has entered a smaller value that can be reliably measured. If a TL response of PD results (at a subsequent visit) then this will be reviewed by the study team blinded to treatment assignment.

Irradiated lesions/lesion intervention

Previously irradiated lesions (i.e. lesion irradiated prior to entry into the study) should be recorded as NTLs and should not form part of the TL assessment.

Any TL (including lymph nodes), which has had intervention during the study (for example, irradiation / palliative surgery / embolisation), should be handled in the following way. Once a lesion has had intervention then it should be treated as having intervention for the remainder of the study noting that an intervention will most likely shrink the size of tumours:

- Step 1: the diameters of the TLs (including the lesions that have had intervention) will be summed and the calculation will be performed in the usual manner. If the visit response is PD, this will remain as a valid response category.
- Step 2: If there was no evidence of progression after step 1, treat the lesion diameter (for those lesions with intervention) as missing and if $\leq 1/3$ of the TLs have missing measurements then scale up as described in the 'Scaling' section below. If the scaling results in a visit response of PD then the patient would be assigned a TL response of PD.
- Step 3: If, after both steps, PD has not been assigned, then, if appropriate (i.e. if $\leq 1/3$ of the TLs have missing measurements), the scaled sum of diameters calculated in step 2 should be used, and PR or SD then assigned as the visit response. Patients with intervention are evaluable for CR as long as all non-intervened lesions are 0 (or $< 10\text{mm}$ for lymph nodes) and the lesions that have been subject to intervention have a value of 0 (or $< 10\text{mm}$ for lymph nodes) recorded. If scaling up is not appropriate due to too few non-missing measurements, then the visit response will be set as NE.

At subsequent visits, the above steps will be repeated to determine the TL and overall visit response. When calculating the previous minimum, lesions with intervention should be treated as missing and scaled up (as per step 2 above).

Scaling (applicable only for irradiated lesions/lesion intervention)

If $> 1/3$ of TL measurements are missing (because of intervention) then the TL response will be NE, unless the sum of diameters of non-missing TL would result in PD (i.e. if using a value of 0 for missing lesions, the sum of diameters has still increased by 20% or more compared to nadir and the sum of TLs has increased by $\geq 5\text{mm}$ from nadir).

If $\leq 1/3$ of the TL measurements are missing (because of intervention) then the results will be scaled up (based on the sizes at the nadir visit to give an estimated sum of diameters) and this will be used in calculations; this is equivalent to comparing the visit sum of diameters of the non-missing lesions to the nadir sum of diameters excluding the lesions with missing measurements.

Example of scaling

Lesion 5 is missing at the follow-up visit; the nadir TL sum including lesions 1 – 5 was 74 mm.

The sum of lesions 1 – 4 at the follow-up is 68 mm. The sum of the corresponding lesions at the nadir visit is 62 mm.

Scale up as follows to give an estimated TL sum of 81 mm:

$$68 \times 74 / 62 = 81 \text{ mm}$$

CR will not be allowed as a TL response for visits where there is missing data. Only PR, SD or PD (or NE) could be assigned as the TL visit response in these cases. However, for visits with $\leq 1/3$ lesion assessments not recorded, the scaled up sum of TLs diameters will be included when defining the nadir value for the assessment of progression.

Lesions that split in two

If a TL splits in two, then the LDs of the split lesions should be summed and reported as the LD for the lesion that split.

Lesions that merge

If two TLs merge, then the LD of the merged lesion should be recorded for one of the TL sizes and the other TL size should be recorded as 0cm.

Change in method of assessment of TLs

CT, MRI and clinical examination are the only methods of assessment that can be used within a trial, with CT and MRI being the preferred methods and clinical examination only used in special cases. If a change in method of assessment occurs, between CT and MRI this will be considered acceptable and no adjustment within the programming is needed.

If a change in method involves clinical examination (e.g. CT changes to clinical examination or vice versa), any affected lesions should be treated as missing. The TL visit response may still

be evaluable if the number of missing TL measurements at a visit is $\leq 1/3$ of the total number of TLs.

3.1.2 Non-target lesions (NTLs) and new lesions – site investigator data.

At each visit, the investigator should record an overall assessment of the NTL response. This section provides the definitions of the criteria used to determine and record overall response for NTL at the investigational site at each visit.

NTL response will be derived based on the investigator’s overall assessment of NTLs as follows:

Table 4 NTL Visit Responses

Visit Responses	Description
Complete response (CR)	Disappearance of all NTLs present at baseline with all lymph nodes non-pathological in size (<10 mm short axis).
Progressive disease (PD)	Unequivocal progression of existing NTLs. Unequivocal progression may be due to an important progression in one lesion only or in several lesions. In all cases, the progression MUST be clinically significant for the physician to consider changing (or stopping) therapy.
Non-CR/Non-PD	Persistence of one or more NTLs with no evidence of progression.
Not evaluable (NE)	Only relevant when one or some of the NTLs were not assessed and, in the investigator's opinion, they are not able to provide an evaluable overall NTL assessment at this visit. Note: For patients without TLs at baseline, this is relevant if any of the NTLs were not assessed at this visit and the progression criteria have not been met.
Not applicable (NA)	Only relevant if there are no NTLs at baseline.

To achieve ‘unequivocal progression’ on the basis of NTLs, there must be an overall level of substantial worsening in non-target disease such that, even in the presence of SD or PR in TLs, the overall tumour burden has increased sufficiently to merit a determination of disease progression. A modest ‘increase’ in the size of one or more NTLs is usually not sufficient to qualify for unequivocal progression status.

Details of any new lesions will also be recorded with the date of assessment. The presence of one or more new lesions is assessed as progression.

A lesion identified at a follow up assessment in an anatomical location that was not scanned at baseline is considered a new lesion and will indicate disease progression.

The finding of a new lesion should be unequivocal: i.e. not attributable to differences in scanning technique, change in imaging modality or findings thought to represent something other than tumour.

New lesions will be identified via a Yes/No tick box. The absence and presence of new lesions at each visit should be listed alongside the TL and NTL visit responses.

A new lesion indicates progression so the overall visit response will be PD irrespective of the TL and NTL response.

If the question ‘Any new lesions since baseline’ has not been answered with Yes or No and the new lesion details are blank this is not evidence that no new lesions are present, but should not overtly affect the derivation.

Symptomatic progression is not a descriptor for progression of NTLs: it is a reason for stopping study therapy and will not be included in any assessment of NTLs.

Patients with ‘symptomatic progression’ requiring discontinuation of treatment without objective evidence of disease progression at that time should continue to undergo tumour assessments where possible until objective disease progression is observed.

